1 BACKGROUND

Aging of the population and prolongation of the lifespan of cardiac patients by modern therapeutic innovations have led to an increased incidence of HF (1). During the last two decades, important progress has been made in the treatment of ambulatory HFrEF patients. Renin-angiotensin system blockers, β -blockers, mineralocorticoid receptor antagonists, ivabradine, neprilysin inhibition, and cardiac resynchronization therapy have all been demonstrated to reduce morbidity and/or mortality in ambulatory HFrEF patients (2-18).

Despite these important advances, many patients are still hospitalized frequently with decompensated HF demonstrating most often signs and symptoms of systemic congestion and volume overload, which is associated with worse outcome (19). Treatment in these cases mainly focuses on symptomatic relief through administration of diuretics, although clear evidence on the optimal agent, dosing schedule, and administration route is lacking. Coexisting renal dysfunction often complicates decongestive treatment and worsening renal function (WRF), often defined as a 0.3 mg/dL rise in serum Cr, is a common finding in this context (20). However, the prognostic impact of WRF defined as Cr change is unsure as it might be associated with worse, neutral or even better outcome (21-23). In contrast, persistent congestion and volume overload, as a reflection of the renal inability to preserve sodium homeostasis, has been more consistently associated with higher mortality and more frequent readmissions in HF (24). This suggests that achieving a net negative fluid balance might be an attractive treatment target in decompensated HF.

Loop diuretics are by far the most commonly used agents to achieve decongestion in decompensated HF. Especially in diuretic-naïve patients, they are often very effective to relieve dyspnoea and congestive symptoms. However, in the Diuretic Optimization Strategies Evaluation (DOSE) trial, which is the only randomized clinical trial on diuretic therapy for decompensated HF patients, no differences in patients' global assessment of symptoms or change in renal function were observed when loop diuretics were administered by bolus as compared with continuous infusion or at high versus low dose during a hospitalization for decompensated HF (25). Also, only a minority of patients (15%) were adequately decongested after 72 h in the DOSE trial, thereby indicating the urgent need for more effective decongestive therapies. Furthermore, guidelines from international cardiac societies lack high-quality data on the optimal dosing, timing and method of delivery of diuretic agents. Importantly, there are several reasons why loop diuretics might be less effective or even harmful in HF. First, loop diuretics directly stimulate renin production by inhibiting the $\text{Na}^+/\text{K}^+/\text{2Cl}^-$ -cotransporter on the luminal side of the macula densa, which depletes intracellular chloride levels in the macula densa. The consequence is an increased cyclooxygenase-2 and nitric oxide synthase I activity in macula densa cells, leading to paracrine prostaglandin E_2 and nitric oxide secretion (26). Both prostaglandin E_2 and nitric oxide work in concert to stimulate renin release by granulosa cells of the afferent arteriole and further detrimental activation of the renin-angiotensin-aldosterone axis. Second, impaired secretion of loop diuretics in the proximal tubules of HF patients, especially when there is concomitant renal dysfunction, results in lower concentrations at the place where these agents act – the luminal side of the thick ascending limb of Henle's loop. Third, increased sodium reabsorption in the proximal tubules might result in less sodium offered to the thick ascending limb

of Henle's loop, especially if glomerular filtration is concomitantly impaired, hampering the efficacy of loop diuretics.

Recent advances in heart failure (HF) biomarker studies suggest promise from markers enhancing traditional method of assessing affected patients. B-type natriuretic peptide (BNP) and its biologically inert, amino-terminal pro-peptide counterpart (NT-proBNP)^{32,33} have quickly become an essential component in the diagnosis and determining prognosis in HF. With a large number of biomarkers now or soon to be available, an understanding of the role that biomarkers may play in HF care is necessary.

2 RATIONALE

From a pathophysiological point of view, targeting sodium reabsorption in the proximal tubules has several potential benefits in HF. First, it is the place where most sodium is reabsorbed, especially in decompensated HF. Second, greater delivery of chloride to macula densa cells decreases renin production, ceasing neurohumoral activation. Third, endogenous natriuretic peptides (acting in the distal nephron) will possibly regain their effects (27). The carbonic anhydrase inhibitor acetazolamide (Diamox®), which is approved for the treatment of mountain sickness, inhibits sodium reabsorption in the proximal tubules. Despite the pathophysiological rationale for inhibition of proximal sodium reabsorption in decompensated HF, acetazolamide is now a largely forgotten diuretic. One observational study in patients with decompensated HF and marked volume overload found that the addition of acetazolamide improved loop diuretic efficacy with ~100 mmol Na⁺ excreted per 40 mg of furosemide equivalent dose (28). Thus, although the diuretic and natriuretic capacity of acetazolamide is poor on its own, it might well be a very efficient booster of diuretic efficacy in combinational diuretic therapy with loop diuretics. This concept is further supported by one small randomized trial including 24 patients with volume overload refractory to loop diuretic therapy (29). All these patients demonstrated a greatly reduced fractional sodium excretion, which was easily overcome by the addition of acetazolamide. We've conducted a small two-center trial to see if improved diuretic efficacy with acetazolamide in a patient population with heart failure and cardio-renal syndrome at high risk for diuretic resistance translates into better natriuresis. (Clinical Trial NCT01973335). The study has just been finished with analysis of the results ongoing. Importantly, the promising concept of blocking proximal nephron sodium absorption with acetazolamide has been published over the last couple of years (30).

The ADVOR study has an innovative primary end-point. As abundant evidence has consistently linked persistent volume overload after decongestive therapy in decompensated HF with poor outcomes, decongestion itself is a valid surrogate end-point (24). It has been demonstrated from reanalysis of the DOSE trial and CARRESS that the persistent oedema has excellent prognostic ability to predict death, readmissions or unscheduled medical contacts (31). In ADVOR, a more exhaustive congestion score with the emphasis on relief of volume overload will be used. Secondary end-points in ADVOR will be very clinically relevant. A more thorough decongestion should also translate into less readmissions for recurrent decompensation, better renal preservation, and eventually lower mortality. This will be assessed as a key secondary end-point after hospital stay. Additionally, time to decongestion is a major determinant of hospital stay and combinational therapy with acetazolamide might significantly shorten this. Finally, improved quality

of life for patients is expected with better decongestion and will be the last secondary end-point. Importantly, acetazolamide is an easy and cheap drug to use (add on, bolus infusion, no special monitoring required), with a potentially favourable cost-efficiency profile. Important health economic data, specifically for the Belgian situation, will be obtained through the ADVOR study.

During the ADVOR study centers can decide to participate in the optional laboratory sub-study. The urine and blood samples collected through this laboratory sub-study will be stored in the University Biobank of Limburg and it will become the biggest databank of its kind within diuretic studies for patients with decompensated heart failure.

This laboratory sub-study will investigate more in detail the mechanistic and potential favourable effect of acetazolamide and loop diuretics. Furthermore, this laboratory sub-study will provide new insights into the pathophysiology of decompensated HF and potentially will allow for identifying a high risk patient population. This could ultimately lead to improved and patient tailored treatment strategies. Biomarker sub-studies have become a valuable source of data for such analysis, and offer unique insights into mechanistic and pathophysiologic pathways in a well selected and phenotyped patient population.

2.1 Assessment and management of risk

The study will examine if the addition of acetazolamide will lead to a better decongestion in decompensated HF patients with volume overload. It's expected that the better decongestion will lead to less HF readmissions, reduced all-cause mortality, improved quality of life, reduced hospital stay duration and significant reduction in HF related health care expenditure.

The ADVOR trial will investigate if adding acetazolamide, which can be very easily administered, in every hospital, without additional extra testing or invasive monitoring, through a bolus infusion in acute decompensated heart failure (ADHF) patients might lead to faster, safer and easier decongestion. If proven beneficial, this approach can easily be adopted by every hospital in a quick manner with considerable cost-savings with regards to health care expenditure and improvements of quality of life for patients.

Importantly, ADVOR will examine if an improved application of existing decongestive therapies (not novel drugs), based on strong scientific reasoning, will result in a better outcome for patients and society. Therefore, data from the study will provide information regarding the safety and efficacy of acetazolamide treatment in above mentioned patient population.

As such, the ADVOR study was specifically designed to have maximum benefit without additional risk for this frail patient population. The study will:

- 1) Be conducted with limited additional testing
- 2) Have minimal or no additional expected risk for the patient (comparison of standard diuretic regimen with standard diuretic regimen + addition of acetazolamide)
- 3) Have very clinically meaningful endpoints. Achieving a faster decongestion with reduced risk for escalation of therapy, which often increases complication rates as well as length of hospital stay.

This will be beneficial for the patients in the short-term. Additionally, a more thorough decongestion should also translate into less readmissions for recurrent decompensation and improved quality of care

Therefore, ADVOR can be considered a 'Low-intervention clinical trial' as:

- 1) Acetazolamide, the investigational medicinal products, which already has been authorised, has a very low risk profile and is well-known to the general cardiologist
- 2) According to the protocol of the clinical trial, Acetazolamide the investigational medicinal product, will be used in accordance with the terms of the marketing authorisation
- 3) The additional diagnostic or monitoring procedures do not pose more than minimal additional risk or burden to the safety of the subjects compared to normal clinical practice

3 OBJECTIVES AND ENDPOINTS / OUTCOME MEASURES

ADVOR will investigate if combination therapy with acetazolamide improves loop diuretic efficacy to increase diuresis in decompensated HF patients with volume overload, allowing for a better/faster decongestion and a lower total dose of loop diuretics. A better / faster decongestion should lead to less HF readmission, reduced all-cause mortality, shorter length of stay and improved quality of life.

3.1 Primary objective

The ADVOR study is a phase IV randomized, multi-center, double-blind study, comparing monotherapy with high-dose loop diuretics (standard of care - SOC) versus combination therapy with acetazolamide and high-dose loop diuretics in patients with decompensated HF and clinical sign(s) of volume overload. While the SOC results in 15% effective decongestion, it's estimated - based on strong scientific reasons - that the combination therapy should have a success rate of 25%, which represents a clear meaningful benefit of 10% more patients with appropriate decongestion after 72 h.

- Population; patients hospitalized with decompensated HF and demonstrating signs of volume overload.
- Intervention: combination therapy with high-dose loop diuretics + acetazolamide
- Comparison: monotherapy with high-dose loop diuretics + placebo
- Outcome: % decongestion, need for escalating diuretic therapy, HF readmission, all-cause mortality, length of stay, QoL
- Time: 72 h for primary endpoint, 3 months for secondary endpoint

3.2 Secondary objectives

1. Combination therapy with acetazolamide improves loop diuretic efficacy to increase diuresis in decompensated HF patients, allowing for a better/faster decongestion and a lower total dose of loop diuretics.
2. Combination therapy with acetazolamide leads to lower occurrence of diuretic resistance and escalating diuretic therapy in decompensated HF
3. Combination therapy with acetazolamide will potentially lead to improved clinical outcome in decompensated HF (less heart failure readmissions, lower all-cause mortality)
4. Combination therapy with acetazolamide will shorten the length of stay in patients with decompensated HF, which is expected to reduce health care expenditure
5. Combination therapy with acetazolamide will potentially lead to improved quality of life

3.3 Endpoints

The ADVOR study has an innovative primary end-point. As abundant evidence has consistently linked persistent volume overload after decongestive therapy in decompensated HF with poor outcomes, decongestion itself is a valid surrogate end-point. It has been demonstrated from reanalysis of the DOSE trial and CARRESS that the persistent oedema has excellent prognostic ability to predict death, readmissions or unscheduled medical contacts. In ADVOR, a more exhaustive yet easy to use – ‘volume

assessment' score - will be used. Importantly, ADVOR will be a double blind randomized trial thereby excluding any potential for bias in the clinical judgement of the treating physician for any of the endpoints including the primary endpoint of decongestion.

Secondary endpoints in ADVOR will be very clinically relevant. A more thorough decongestion should also translate into less readmissions for recurrent decompensation, and eventually lower mortality. This will be assessed as a key secondary end-point after hospital stay. Additionally, time to decongestion is a major determinant of hospital stay and combinational therapy with acetazolamide might significantly shorten this. Finally, improved quality of life for patients is expected with better decongestion and will be the last secondary endpoint. Importantly, acetazolamide is an easy drug and very cheap drug to use (add on, bolus infusion, no special monitoring required), which will therefore be easily adopted by the health care. Endpoints have also been discussed with "Mon Coeur Entre Parenthèses" which is a HF patient association (VZW) representing HF patients and their peers and deemed to be important by them.

In addition, the primary and secondary outcome measures are in line with the COMET (Core Outcome Measures in Effectiveness Trials) initiative. Indeed 'decongestion' (being dry is for the patient a very important improvement in symptomatology), heart failure readmission, all-cause mortality, length of stay and quality of life can all be considered standardised relevant core outcomes sets. Therefore, the core outcomes relevant for any acute heart failure study will be collected and reported, making it easier for the results of ADVOR to be compared, contrasted and combined as appropriate with other trials (Zannad F et al, European Journal of Heart Failure, 2013;15:1082-1094). Additionally, we will continue to explore other tertiary outcomes, which are often mechanistically very interesting, as well.

We will also collect the dosages of neurohumoral blocker therapy throughout the study period, thereby hopefully facilitating a better implementation of guideline recommended therapy. As guidelines recommend a specific dosage for each of these drugs in HFrEF, it's easy to standardize the intake of such medications to be used in an accurate analysis. This will be done as an exploratory tertiary end-point.

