7.7 Treatment phase assessments

7.7.1 Day 1

- Request patient to empty their bladder before administration of the first dose of loop diuretics.
- Administer the first bolus of loop diuretics and acetazolamide or placebo to the patient.
- Start the urinary collection immediately after first bolus of loop diuretics and acetazolamide or placebo is administered. The collection will stop the latest as close to but prior to the morning bolus of study medication on day 3. Urinary catheter insertion is strongly recommended but not mandatory to achieve an optimal urine collection. However, in case of urinary incontinence, placement of a urinary catheter is mandatory. Care should be taken to ensure ALL urine is collected. For more details regarding the study urinary collection see [appendix 4](#).

If the patient is enrolled between midnight and 6 a.m., day 1 assessments and day 2 assessment can be performed on the same day but only if there is a difference of minimum 6 hours between the start of the study medication on day 1 and study medication on day 2.

7.7.2 Day 2, Day 3 and Day 4

- Collect vital signs including body weight, arterial blood pressure, heart rate
- As long as patient is assessed as volume overloaded during the previous volume assessment, perform volume assessment by the Principal Investigator or a Sub-investigator who has been trained in the study volume assessment (Figure 3 in section 8)
- Collect morning blood sample for local laboratory assessment: serum haemoglobin, haematocrit, electrolytes (Na, K, Cl, HCO₃), serum urea, serum Cr, serum albumin.
- On the morning of Day 2 and Day 3, collect an urine sample from urine collection period 1 and period 2 respectively for analysis in local lab. In case patient is participating in the optional laboratory sub-study, collect an additional urine sample for each urine collection period for shipment to the University Biobank Limburg for storage and additional research (see [section 7.10](#)). Urinary collection will stop at the morning of day 3 ([appendix 4](#)).
- In case patient is still volume overloaded continue study treatment as described in [section 8](#)
- Collect concomitant medication ([see Appendix 5](#))
- Document and assess adverse events ([section 9](#))
- In addition, on the morning of day 4 or at discharge (whatever comes first):
 - EQ-5D to be completed by the patient.

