8.1 Name and description of intervention(s)

At randomization

At the moment of randomization, oral loop diuretics are stopped and the patient receives an IV bolus of loop diuretics at a dose equal to the double of his oral daily maintenance dose* with a maximal dose of 5 mg bumetanide (=200 mg furosemide). Bumetanide is the preferred loop diuretic agent to be used in this trial.

Conversion factor:

1 mg bumetanide po = 1 mg bumetanide IV

40 mg furosemide po = 40 mg furosemide IV

20 mg torsemide po = 40 mg furosemide IV = 1 mg bumetanide IV

Some examples are listed below:

- *if a patient takes 1x1 mg bumetanide po, the patient will receive 2x1x1 mg = 2 mg bumetanide IV*
- *if a patient takes 2x2,5 mg bumetanide po, the patient will receive 2x2x2,5 mg = 5 mg bumetanide IV*
- *if a patient takes 1x40 mg furosemide po, the patient will receive 2x1x40 mg = 80 mg furosemide IV*
- *if a patient takes 1x80 mg furosemide po, the patient will receive 2x1x80 mg = 160 mg furosemide IV*
- *if a patient takes 1x20 mg torsemide po, the patient will receive 2x1x1 mg bumetanide IV = 2 mg bumetanide IV or 2x1x40 furosemide IV = 80 mg furosemide IV*

Together with this initial dose of loop diuretics patients will receive an intravenous bolus of 500 mg of acetazolamide or placebo.

START DOSE (IV) = 2 x orally daily maintenance dose* of loop diuretics (max. 5 mg of bumetanide)

+

500 mg acetazolamide or placebo

**If the oral daily maintenance dose has changed over the week prior to randomization, it will be defined as the highest orally administered daily dose that the patient has received in an outpatient context 3 days prior to randomization.*

During the treatment phase

[figure not shown]
Between administering the start dose and next treatment dose a minimum of 6 hours is required. During the remaining part of the treatment phase, the patient will continue to receive 2 treatment doses every day provided that the treating physician has concluded during the morning rounds that the patient is still volume overloaded (see Figures 2+3). The dose will be the orally daily maintenance dose, administered between 8:00 and 12:00 am, together with an intravenous bolus of 500 mg of acetazolamide or placebo. The second dose of loop diuretics, again the orally daily maintenance dose, will be given 6 hours after the morning dose.

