In case of **metabolic acidosis** with serum bicarbonate levels <20 mmol/L, it is recommended to administer intravenously 100 ml of NaHCO_3 8.4%.

Treatment with **neurohumoral blockers** (e.g. renin-angiotensin system blockers, sacubitril/valsartan, beta-blockers, and mineralocorticoid receptor antagonists) may be continued at the same or lower dosage at the discretion of the treating physician, until the end of the treatment phase (max 4 days) or until complete decongestion is achieved, whatever comes first. Dose increases for any of these medications are not allowed during the screening and treatment phase with the exception of mineralocorticoid receptor antagonists in case of hypokalaemia despite intravenous potassium supplement. In addition, starting an SGLT2 inhibitor and a switch from renin-angiotensin system blockers to sacubitril/valsartan is not allowed during the screening and treatment phase, but might be pursued after decongestion is achieved. After decongestion, it is strongly recommended to up-titrate doses of neurohumoral blockers according to the guidelines in the HFrEF patients. Dosages of neurohumoral blockers are collected at screening, at discharge and at three months follow-up.

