4.4 Endpoint adjudication

Because the primary endpoint requires physical examination of the blinded study physician, adjudication of the primary event is not possible. However, all admission labelled as HF readmission, all-cause mortality and the need for renal replacement therapy will be adjudicated by the Endpoint Adjudication Committee (EAC)

For the endpoints HF readmission, all-cause mortality and the need for renal replacement therapy a complete endpoint package will need to be send to the sponsor. This package should include anonymized source documents (SDs) relevant to the endpoint reported (e.g. discharge letter, emergency room notes, etc). The SD should include at least the reason for admission/death and the received treatment for the event (if applicable). This package will be assessed by the Endpoint adjudication members of the Endpoint adjudication committee.

In case of discrepancy between the evaluation of the EAC members regarding the same event, the Trial Data Manager will contact the EAC members to inform them on the discrepancies found so the both of them can come to a final decision. The discrepancies and the final decision will be documented.

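### Protocol 3.3 says blinding rules out any bias in the primary endpoint, but same-morning bicarbonate is unmasked and no rule puts the volume score first

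*Combined protocol and SAP*

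**What the plan says.** - **The claim.** Protocol v2.0, 3.3, relies on double-blinding, "thereby excluding any potential for bias in the clinical judgement of the treating physician", and extends this to every endpoint, the primary one included.
- **Who scores.** Section 7.7.2 has sites "perform volume assessment by the Principal Investigator or a Sub-investigator who has been trained in the study volume assessment" on days 2, 3 and 4 while the patient remains overloaded. Section 8.1 continues study dosing "provided that the treating physician has concluded during the morning rounds that the patient is still volume overloaded". Section 11.1 asks that, as far as possible, one person make all subjective assessments of a patient.
- **What is measured that morning.** Section 7.7.2 also says "Collect morning blood sample for local laboratory assessment", and its list includes bicarbonate.
- **What is done with it.** Under Background therapy in 8.1, for metabolic acidosis "with serum bicarbonate levels <20 mmol/L, it is recommended to administer intravenously" sodium bicarbonate. Under Stop treatment, acidosis with pH below 7.2 is one of the events that permit, but do not oblige, the physician to stop.
- **How the score is used.** SAP v2.0, 4.1.2, counts a score of 1 or less on day 2 or day 3 as success. On day 4 it also requires that escalation was not needed on day 3. Protocol 8.1 cancels the next morning's assessment once a patient is scored as decongested.
- **Adjudication.** SAP v2.0, 4.4: "Because the primary endpoint requires physical examination of the blinded study physician, adjudication of the primary event is not possible".

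**The concern.** Blinding by matched vials protects the endpoint only if nothing else the assessor sees during treatment points to the arm. Here a laboratory value plausibly related to the drug's mechanism becomes available on the mornings when a partly subjective score decides the primary outcome. If an assessor suspects the allocation, a borderline oedema grade could be scored differently by arm. Because a score of 1 or less on day 2 or day 3 settles success and is not rechecked the next morning, one such call can fix a patient's outcome. A shift in one direction would inflate the false-positive rate. A shift in the other would cost power.

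**Working it through.** **1. Does the text rule out the pathway?**

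| Link | Where | Status |
|---|---|---|
| Scorer may be on the treating team | Protocol 7.7.2, 8.1 | Permitted; neither required nor excluded |
| Bicarbonate drawn on scoring mornings | Protocol 7.7.2 | Stated |
| Bicarbonate open to the treating team | Protocol 8.1 (supplement advice) | Follows, since they are advised to act on it |
| Bicarbonate related to the drug | Protocol 2 (drug class); acidosis in Protocol 3.6 and 8.1 and SAP 4.1.4 | Inferred; no passage says acetazolamide lowers it |
| Score recorded before results are read | Protocol 7.7.2, 7.9 and footnotes | No rule; the bullet order in 7.7.2 is only a list |
| Independent check of the score | SAP 4.4 | None for the primary endpoint |

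No link is closed by the text, so the absolute statement in 3.3 is unsupported.

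**2. Which judgement is exposed?** Protocol 8.1 requires chest X-ray or echography to confirm residual effusion or ascites. Oedema has no such check. Trace oedema scores 1 and clear pitting oedema scores 2, so that boundary decides success when effusion and ascites are absent.

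**3. The plan's own sample size.** Inputs from SAP 4.5 and 5.1: 15% versus 25%, two-sided alpha 0.05, power 80%. With unpooled variance:

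n per arm = (1.960 + 0.842)² × (0.15×0.85 + 0.25×0.75) / 0.10² = 7.849 × 0.315 / 0.01 = 247.2

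Twice this is 494.5 (stated: 494), and 494 × 1.05 = 518.7, so 519. The sample size reproduces and is not at issue.

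**4. Illustration of sensitivity.** The documents give no rate of unblinding or mis-scoring, so the shift d is an assumption. Take no true effect, 15% in the control arm, 15% + d in the acetazolamide arm, and 259 per arm (519/2, rounded down). A two-proportion normal test stands in for the mixed logistic model.

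For d = 2 points:
- Mean proportion 0.16; null SE = √(2 × 0.16 × 0.84 / 259) = 0.0322; critical difference = 1.96 × 0.0322 = 0.0631
- Actual SE = √((0.15×0.85 + 0.17×0.83) / 259) = 0.0322
- Upper tail: (0.0631 − 0.02) / 0.0322 = 1.34, giving 9.0%
- Lower tail: (−0.0631 − 0.02) / 0.0322 = −2.58, giving 0.5%
- Two-sided type I error ≈ 9.5%

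| Assumed shift | Patients of 259 | Type I error |
|---|---|---|
| 0 | 0 | 5.0% |
| 1 point | 2.6 | 6.1% |
| 2 points | 5.2 | 9.5% |
| 3 points | 7.8 | 15.1% |
| 5 points | 13.0 | 32.2% |

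With 247 per arm, the 2-point figure is 9.3%.

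**5. The opposite direction.** With a true 15% versus 25%, 247 per arm and scoring that leans against the drug, power falls from 79.5% to 71.5%, 62.1% or 51.7% for shifts of 1, 2 or 3 points.

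**The case against.** The case on the other side is substantial.

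- **Several stronger readings fail.** A reader might infer that the team must act on low bicarbonate, but the supplement is only recommended and stopping is optional. A reader might infer that the plan names acidosis as an expected effect of acetazolamide, but its acidosis rules and endpoints apply to both arms and none attributes acidosis to the drug. A reader might infer that the scorer reads bicarbonate first, but no passage says so, and Protocol 7.1.1 allows for a treating physician outside the study team.
- **There are real safeguards.** These are imaging for effusion and ascites, a measured 3500 mL urine threshold in the escalation rule, assessor training, and drug and placebo presented alike (8.5). They narrow the exposure but leave the oedema grade unprotected. New effusion or ascites needs imaging only if it is scored, and the urine threshold applies only to patients still judged overloaded.
- **The shifts are hypothetical.** This stands. The arithmetic would apply to any subjective endpoint and does not show that bicarbonate moves scores.
- **The remedy is partial and late.** Withholding one morning's result leaves earlier values known. SAP 5.10.4 reports that the trial was completed, so a procedural change cannot alter data already collected.
- **The Manual of Operations might set an order.** It is not among the documents, so this cannot be checked.

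None of this rescues the absolute claim in 3.3, which is what the protocol offers in place of a scoring-order rule.

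**Conclusion.** The point holds as a gap between claim and design. Section 3.3 says the potential for bias is excluded, whereas the procedures leave a plausible route to partial unblinding of the person who scores the primary endpoint. The conclusion rests on two inferences: that the scorer may see the treating team's laboratory results, and that a carbonic anhydrase inhibitor shifts bicarbonate enough to be noticed.

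A reader might go further and conclude that the primary result is biased in favour of acetazolamide. The documents do not support that: they give no size, no direction and no evidence that unblinding occurred. The 9.5% figure shows only that about five patients reclassified in one arm would nearly double the nominal error. It does not estimate what happened. This is a cheap improvement to the plan, not a defect that invalidates it.

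**What to change.** - **Protocol 7.7.2:** require the volume score to be recorded and time-stamped in the eCRF before that morning's laboratory results are opened. All results stay available to the treating team for safety, and no clinical rule changes.
- **Protocol 3.3:** replace the statement that bias is excluded with one that double-blinding is *reducing the potential for bias*. On its own this rewording changes no procedure.

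The cost is one sentence in each section and an eCRF time stamp; no extra assessor is needed. The limit is that on days 3 and 4 earlier on-treatment bicarbonate values are known, and the clinician needs the day-3 urine volume for the escalation decision (Appendix 4). The risk is therefore reduced, most fully for the day-2 score, which precedes any scheduled on-treatment result, but it is not removed. For data already collected, the remaining step is to report this as a limitation of the blinding.
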